7.4 Rescue Medications

The following medications may be used to treat an allergic reaction:

- Epinephrine 1 mg/mL; 0.3 – 0.5 mg intramuscularly

- β -adrenergic agonist inhaler or nebulizer (e.g., albuterol)
- Antihistamines
- Steroids
- Intravenous fluids
- Oxygen

Guidelines for the treatment of systemic allergic reactions are detailed in the Manual of Procedures (MOP). Rescue medications should be recorded on the Concomitant Medications eCRF.

8. Study Procedures

8.1 Adult Stage 1 Study Procedures

8.1.1 Visit Windows

Appendix 20.1, [Table 17](#) presents the Schedule of Events for participants in Adult Stage 1. The visit windows are defined below:

- Screening until Randomization/Allocation: up to 21 days from time of obtaining informed consent until the participant is determined to meet study entry criteria (allocation for Cohort C) or randomization (for Cohorts A and B).
- Randomization: phone visit that must occur at least 7 days prior to administration of the additional homologous vaccine dose at the Baseline/Week 0 visit for Cohorts A and B.
 - See Section 8.1.2.4 Randomization/Allocation for more details on Randomization visit activities.
- Baseline (Week 0/Day 1)
 - See Section 8.1.3 Baseline (Week 0/Day 1) Visit for more details on Baseline visit activities.
- Week 1: Vaccine Diary Review Phone Visit (Day 8 – Day 12)
- Week 4: (+/- 1 week)
- Week 12: (+/- 2 weeks)
- Week 24: (+/- 2 weeks)
- Week 36: (+/- 2 weeks)
- Week 48 (End of Study): (+/- 2 weeks)

8.1.2 Screening and Randomization/Allocation

8.1.2.1 Pre-Screening

An optional Pre-Screening visit may be conducted to confirm that a participant has had a negative or suboptimal response to initial COVID-19 vaccine regimen prior to Screening. This study will be explained in lay language to each potential participant. Each participant will sign an informed consent form before committing to study Pre-Screening procedures. Pre-Screening procedures at the study site will vary by method of recruitment as outlined below:

Study site personnel are responsible for the following:

1. Consent the participant for an ACV01 Pre-Screening Evaluation.
2. Conduct the rapid result or other antibody testing.
3. Invite the participant to an ACV01 Screening Visit if the result is negative or weakly positive per the site preferred antibody test method.

8.1.2.2 Determination of Participant Cohort and Identification of Qualifying Disease

Prior to screening a potential participant, the site needs to determine which IS Cohort the participant will be assigned to and identify the participant's qualifying autoimmune disease.

Cohorts: The ACV01 study will be accepting participants who are taking 3 types of IS medications: MMF or MPA, MTX, and BCDTs. The criteria for assignment to each cohort are listed below:

- Cohort A: Receipt of MMF or MPA (\pm other rheumatic disease medications, including biologics)
 - Participants who are taking MMF or MPA will be placed in this cohort.
 - Participants may not also be taking MTX.
 - Participants may not have taken anti-CD20 and anti-CD19 BCDT in the past 18 months.
- Cohort B: Receipt of MTX (\pm other rheumatic disease medications, including biologics)
 - Participants who are taking MTX will be placed in this cohort.
 - Participants may not also be taking MMF/MPA.
 - Participants may not have taken anti-CD20 and anti-CD19 BCDT in the past 18 months.
- Cohort C: Receipt of anti-CD20 or anti-CD19 BCDT within the past 18 months (\pm other rheumatic disease medications)
 - Participants who have taken B cell depletion medications in the past 18 months will be placed in this cohort.
 - Participants may also be taking MMF/MPA or MTX.

Qualifying Autoimmune Diseases: The ACV01 Adult Stage 1 study will be accepting adult participants diagnosed with SLE, RA, MS, SSc, or pemphigus. In the event that a participant has more than one of these 5 diseases, disease activity assessments will be collected throughout the trial for only the disease associated with IS medication cohort assignment at entry into the trial.

8.1.2.3 Screening

The research study will be explained in lay terms to each potential Stage 1 participant. The potential participant will sign an Institutional Review Board (IRB)-approved informed consent form before undergoing any study procedures. Once the informed consent has been signed, the participant will be assigned a unique participant number. At this time, study-specific procedures may be performed.

The purpose of the screening period, which begins at the time of signed consent, is to confirm eligibility to enter the study. All screening procedures, assessments, and laboratory measures to determine participant eligibility will be conducted within a 21-day screening window with shorter time periods expected for most participants.

The assessment of eligibility may take a series of visits that occur on separate days. The Screening visit biomarkers should reflect, as much as possible, the biometrics of the participant prior to any study procedures.

The following procedures, assessments, and laboratory measures will be conducted:

1. Informed Consent
2. Demographics
3. Medical History
4. Concomitant Medications (including contraceptives)
5. Comprehensive Physical Exam
6. Vital Signs

7. Confirmation of Disease Classification Criteria Assessment
 - a. 2019 ACR/EULAR or 2012 SLICC classification criteria for SLE
 - b. 2010 ACR/EULAR classification criteria for RA
 - c. 2013 EULAR/ACR classification criteria for SSc
 - d. 2017 McDonald diagnostic criteria for MS
 - e. International consensus criteria for pemphigus
8. Complete assessments of disease activity: H-SLEDAI and PGA for SLE; DAS28-CRP and PtGA for RA; patient self-reported disease flare and Modified Rodnan Skin Score for SSc; physician-assessed relapse for MS; PDAI for pemphigus
9. Review of initial COVID-19 vaccination record and antibody response
10. Central laboratory assessments for all participants
 - a. Infectious Disease Testing: HIV, Hepatitis B surface antigen, Hepatitis C antibody with viral load if indicated
 - b. Elecsys® Anti-SARS-CoV-2 S assay to assess response to initial COVID-19 vaccine regimen
 - c. Complete blood count (CBC) with differential
 - d. Comprehensive metabolic panel (CMP), estimated glomerular filtration rate (eGFR)
11. Local laboratory assessments for all participants
 - a. Molecular COVID-19 Testing:
 - b. Urine pregnancy test (women of child-bearing potential only)
12. Disease-specific laboratory assessments:
 - a. RA participants only
 - i. C-Reactive Protein (CRP)
 - b. SLE participants only
 - i. Anti-dsDNA, C3, C4
 - ii. Random urine protein-creatinine ratio
 - iii. Urinalysis (microscopic)
 - c. B-cell depleting therapy participants only
 - i. If on CD20 depleting agent, CD19+ B cells
 - d. Pemphigus participants only
 - i. Anti-desmoglein 1/3 IgG autoantibodies by enzyme-linked immunosorbent assay (ELISA)
13. Inclusion/Exclusion criteria assessment

Participants with abnormal laboratory values that prohibit entry may be re-tested once during the screening period, which may last up to 21 days. Participants who screen fail may be rescreened one time and must repeat all screening assessments. Any further rescreening activity requires approval by the medical monitor.

During the Screening visit, the site will review vaccine eligibility criteria, per Section 8.1.3 Baseline Visit with the participant.

8.1.2.3.1 Evaluation of Eligibility and Randomization/Allocation

Cohorts A (MMF/MPA) or B (MTX): If the participant meets all eligibility criteria, then proceed as follows:

- Schedule Baseline/Week 0 Visit (within 28 days of first Screening assessment).
- Randomize the participant (within 21 days of screening and at least 7 days prior to the scheduled Baseline/Week 0 visit).

Cohort C (BCDT): If the participant meets all eligibility criteria, then proceed as follows:

- Schedule Baseline/Week 0 Visit (within 28 days of first Screening assessment).

8.1.2.4 Randomization/Allocation

Randomization is a phone visit that will occur up to 21 days after Screening and at least 7 days prior to the Baseline/Week 0 visit for participants in Cohorts A (MMF/MPA) and B (MTX). During Randomization, sites will call participants to confirm that concomitant medication and medical history data continue to meet eligibility criteria. After eligibility is confirmed, the site will randomize the participant to an IS medication treatment plan per Section 3.1 Description of Study Design. If the participant is randomized to withhold cohort-defining IS medication treatment, the site will communicate the details of the medication hold to the participant per Section 7.1.1 Protocol-mandated Medications. The site will inform the participant that there should be no changes to his/her other existing medications between Randomization and the Baseline/Week 0 visit.

For Stage 1, allocation is the confirmation that participants in Cohort C have met all study entry criteria and may proceed to the Baseline/Week 0 visit. The site will inform the participant that there should be no changes to his/her other existing medications between Allocation and the Baseline/Week 0 visit.

8.1.3 Baseline (Week 0/Day 1) Visit

Eligible participants who meet all inclusion criteria and none of the exclusion criteria will proceed with visits and assessments according to Section 20.1 Schedule of Events. Eligible participants will be assessed for disease activity and SARS-CoV-2 infection at the Baseline/Week 0 visit, prior to receipt of an additional homologous vaccine dose. Prior to administering the additional homologous vaccine dose at the Baseline visit, the site will confirm the participant meets vaccine eligibility per the criteria below:

- No increase to the permitted concomitant medications in participants in Cohorts A and B between Randomization and Baseline/Week 0.
- No B-cell depletion infusions or changes in permitted concomitant medications in participants in Cohort C between allocation and Baseline/Week 0.
- No clinically active disease (including myocarditis or pericarditis) at Baseline/Week 0 resulting in an increase/addition of IS medications. For participants with MS, no suggestion of a MS relapse per the investigator.
- No active myocarditis or pericarditis based on review of clinical symptoms.
- No positive molecular COVID-19 test at Baseline/Week 0.
- No increase in oral, intramuscular, or intravenous steroids within 14 days of Baseline/Week 0.

If the vaccine cannot be administered at the Baseline/Week 0 visit, it must be administered during the following 2-3 days. Vaccine eligibility will be confirmed prior to administration of the vaccine. **Administration of the additional homologous vaccine dose must occur within 28 days of the Screening visit.**

If a participant is not eligible to receive the additional homologous vaccine dose at Baseline/Week 0, he/she will be terminated from the study. The participant may rescreen under a new participant ID after 30 days from the determination of vaccine ineligibility. Participants who were randomized to withhold cohort-defining IS medications before the Baseline visit and who are not eligible to receive an additional homologous vaccine dose at that visit, may restart their IS medications immediately. The participant will be replaced.

See Section 8.1.4 Study Procedures and Assessments for more information on individual clinical and research assessments.

If the participant is randomized to the withhold cohort-defining IS medication treatment plan, the site will call the participant after the Baseline visit to provide instructions on resuming IS medication per Section 7.1.1 Protocol-mandated Medications.

8.1.4 Study Procedures and Assessments

8.1.4.1 General Assessments

- **Informed Consent Process**
- **Demographics.** Participants should provide demographic information. In particular, race and ethnicity should be self-identified.
- **Medical History.** Medical history will be performed as part of screening activities and standard medical care. The medical history assessment will include current illnesses/conditions and past medical history.
- **Concomitant Medications (including contraceptives).** A current list of prescription and over-the-counter medications, supplements, and treatments will be obtained. Assessment of eligibility should include a review of permitted and prohibited medications. The medication, dose, frequency, route, start date, stop date, and indication should be captured.
- **Comprehensive Physical Examination (Screening Only).** Physical examinations are to include, at least, the following systems: general appearance, skin, head/eyes/ears/nose/neck/throat, respiratory/chest, cardiovascular, abdominal, neurological, & musculoskeletal/extremities.
- **Targeted physical examination:** to be guided by participant complaints and prior abnormalities.
- **Neurological Exam:** for all MS participants and for participants with other diagnoses who have a neurological complaint after Screening.
- **Vital Signs.** Height will only be collected at Screening. Weight, temperature, pulse, and blood pressure will be collected at each visit. Vital signs should be obtained with the participant in a seated position, and prior to taking samples for laboratory testing at applicable study visits.
- **Adverse Events**
- **Vaccine Reaction Diary Overview, Training, & Distribution:** Participants will be provided access to an electronic 7-day diary to aid in recording solicited local and systemic reactions to the vaccine, as well as symptoms of a potential allergic reaction, unsolicited AEs, and concomitant medications, including start and stop dates. The diary will include instructions for participants on how to take an oral temperature and how to measure injection site reactions. A paper copy of the diary may be provided for participants who do not have a device to access the electronic diary or as a backup collection tool. A member of the study team will review the information in the diary with the participant, including how to use and access the electronic diary. As some solicited adverse events and grading scales are age-dependent and apply only to the pediatric population, separate age-specific Pediatric Vaccine Reaction Diaries will be provided to pediatric participants.

8.1.4.2 Disease-Specific Assessments

- **SLE Disease Assessments**
 - H-SLEDAI
 - Thanou modified SELENA-SLEDAI Flare Index
- **SSc Disease Assessments**
 - Flare assessment for SSc (including patient reported flare assessment)

- Modified Rodnan Skin Score
- **MS Disease Assessments**
 - Physician-assessed relapse for MS
 - Expanded Disability Status Scale (EDSS [at Baseline/Week 0])
 - If an MS relapse is suspected, the EDSS will be assessed at the following time points:
 - Time of suspected relapse
 - Time of relapse recovery (to occur 8-12 weeks after the suspected relapse EDSS assessment)
- **RA Disease Assessments**
 - DAS28-CRP
- **Pemphigus Disease Assessments**
 - PDAI
 - Flare assessment for pemphigus

8.1.4.3 Participant- and Clinician-reported Outcomes

- **Participant Reported Outcomes**
 - PROMIS-29
 - PtGA
 - PGI-C
- **Clinician Reported Outcomes**
 - PGA
 - CGI-C

8.1.4.4 Clinical Laboratory Assessments

Blood and urine for the clinical laboratory assessments listed below will be collected per Section 20.1 Schedule of Events. The results will be evaluated for safety by the site investigator. Abnormal tests that meet grading and reporting criteria will be reported as adverse events (See Section 12.3 Grading and Attribution of Adverse Events).

- **Local Laboratory Assessments**
 - **Pregnancy Testing (Women of Childbearing Potential Only).** Urine pregnancy test at Screening and Baseline/Week 0 visit.
 - **Molecular COVID-19 Testing** Baseline/Week 0/Day 1 molecular COVID-19 Testing can be collected and run and the results reported by a community-based laboratory (national chain pharmacy, Local MD office, State or Local Government run testing center, Urgent Care Center) not listed on the 1572. This test must be performed within the 48 hours prior to the Baseline/Week 0/Day 1 visit. For additional details, please see the ACV01 Manual of Procedures.
- **Central Laboratory Assessments**
 - **Hematology**, including complete blood count (CBC) with differential.
 - **Blood Chemistry** including CMP, eGFR.

- **Detection of antibodies against SARS-CoV-2 Spike protein (IgG)** using the Roche Elecsys® Anti-SARS-CoV-2 S electrochemiluminescence immunoassay intended for qualitative and semi-quantitative detection of antibodies to SARS-CoV-2 spike protein (RBD) in human serum.
- **Disease-specific laboratory assessments:**
 - RA participants only
 - C-Reactive Protein (CRP)
 - SLE participants only
 - Anti-dsDNA, C3, C4
 - Random urine protein-creatinine ratio
 - Urinalysis: microscopic
 - B-cell depleting therapy participants only
 - If on CD20 depleting agent, CD19+ B cells
 - Pemphigus participants only
 - Anti-desmoglein 1/3 IgG autoantibodies by ELISA

8.1.4.5 Mechanistic Specimens

- Serum
 - Antibody levels will be tested at each time point to test for IgG and immunoglobulin M (IgM) responses against SARS-CoV-2 spike, receptor binding domain, and nucleocapsid proteins.
- Whole blood/peripheral blood mononuclear cell (PBMC)/plasma/DNA
- RNA assays

8.1.5 Unscheduled Visits

If disease activity increases or other concerns arise between regularly scheduled visits, participants should be instructed to contact study personnel and may be asked to return to the study site for an “unscheduled” visit.

8.1.6 Early Termination

An Early Termination Visit should be requested for participants who withdraw from the study prior to study completion. Assessments to be conducted at an early termination visit can be found in Section 20.1 Schedules of Events.

8.2 Adult Stage 2 Study Procedures

8.2.1 Visit Windows

8.2.1.1 Visit Windows for Adult Stage 2 Newly Recruited Participants

Appendix 20.1, [Table 18](#) presents the Schedule of Events for participants who are newly recruited to Adult Stage 2. The visit windows are defined below:

- Screening and Allocation: 28 to 7 days prior to the S2 Baseline/Week 0 visit.
- Baseline (Week 0/Day 1)
 - See Section 8.2.4 Baseline (Week 0/Day 1) Visit for more details on Baseline/Week 0 visit activities.
- Week 1: Vaccine Diary Review Phone Visit (Day 8 – Day 12)
- Week 4: (+/- 1 week)

- Week 12: (+/- 2 weeks)
- Week 24: (+/- 2 weeks)
- Week 36: (+/- 2 weeks)
- Week 48 (End of Study): (+/- 2 weeks)

8.2.1.2 Visit Windows for Adult Stage 2 Rollover Participants

Participants can roll over into Stage 2 via two pathways:

- Stage 1 participant rolls over to Stage 2
 - A Stage 1 participant who has a Roche Elecsys result ≤ 2500 U/mL at a post-Baseline visit may elect to roll over into Stage 2, starting the Stage 2 schedule of events for rollovers.
- Stage 2 participant rolls over to a different Stage 2 treatment arm
 - A Stage 2 participant who received an alternative mRNA vaccine dose and has a Roche Elecsys result ≤ 2500 U/mL at a post-Baseline visit may elect to re-enter Stage 2, restarting the Stage 2 schedule of events for rollovers.

For participants rolling into Adult Stage 2, the visit windows are defined below.

- Total Screening Period:
 - Up to 28 days from the Stage 1 or Stage 2 Visit at which negative, suboptimal or low immune response to the previous COVID-19 vaccine was obtained until the S2 Baseline/Week 0 visit.
 - If the S2 Baseline/Week 0 visit cannot be conducted within 28 days of the qualifying Follow-up Visit noted above, the participant will return to the site for a full S2 Screening visit, as described in Section 8.2.2.3.2 Screening for Adult Stage 2 Rollover Participants.
 - S2 Screening Phone Visit: at least 7 days prior to administration of the alternative vaccine at S2 Baseline/Week 0.
 - See Section 8.2.2.3.2 Screening for Adult Stage 2 Rollover Participants for more details on the screening procedures for rollover participants.
- S2 Baseline (S2 Week 0/Day 1)
 - See Section 8.2.4 Baseline (Week 0/Day 1) Visit for more details on the S2 Baseline/Week 0 visit activities.
- S2 Week 1: Vaccine Diary Review Phone Visit (Day 8 – Day 12)
- S2 Week 4: (+/- 1 week)
- S2 Week 12: (+/- 2 weeks)
- S2 Week 24: (+/- 2 weeks)
- S2 Week 36: (+/- 2 weeks)
- S2 Week 48 (End of Study): (+/- 2 weeks)

8.2.2 Screening and Allocation

8.2.2.1 Pre-Screening

8.2.2.1.1 Pre-Screening for Adult Stage 2 Newly Recruited Participants

An optional Pre-Screening visit may be conducted to confirm that a participant has had a negative, suboptimal, or low immune response to initial COVID-19 vaccine regimen prior to Screening. This study will be explained in lay language to each potential participant. Each participant will sign an informed consent form before committing to study Pre-Screening procedures. Pre-Screening procedures at the study site will vary by method of recruitment as outlined below:

Study site personnel are responsible for the following:

1. Consent the participant for an ACV01 Pre-Screening Evaluation.
2. Conduct the rapid result or other antibody testing.
3. Invite the participant to an ACV01 Screening Visit if the result is negative or weakly positive per the site preferred antibody test method.

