3.5.1 Adult Population

3.5.1.1 Adult Stage 1

Participants who sign the informed consent form and meet all eligibility criteria for Adult Stage 1 will be assigned to cohorts defined by IS medication (Cohort A: MMF/MPA; Cohort B: MTX; and Cohort C: BCDT) and by the initial COVID-19 vaccine regimen received (Moderna COVID-19 Vaccine, Pfizer-BioNTech COVID-19 Vaccine, or Janssen COVID-19 Vaccine). Participants in Cohort C will be allocated to continuing to take their prescribed IS medications throughout the trial. Participants in Cohorts A and B will be randomized in a balanced fashion (1:1), within the cohorts defined by IS medication and initial COVID-19 vaccine regimen, to one of the available IS medication treatment plans (continue cohort-defining IS vs. withhold cohort-defining IS). Randomization will be performed using a permuted block design stratified by disease type.

A total of 60 participants with a Roche Elecsys® Anti-SARS-CoV-2 S result ≤ 200 U/mL will be randomized or allocated to each arm. In each arm, the number of participants with Roche Elecsys® Anti-SARS-CoV-2 S results ≤ 50 U/mL will be capped at 40 participants, and the number of participants with Roche Elecsys® Anti-SARS-CoV-2 S results > 50 U/mL and ≤ 200 U/mL will be capped at 40 participants.

3.5.1.2 Adult Stage 2

Participants who have signed the informed consent form and meet all eligibility criteria for Adult Stage 2 will be allocated to cohorts defined by IS medication (Cohort D: MMF/MPA; Cohort E: MTX; and Cohort F: BCDT) and by the previous COVID-19 vaccine regimen. See Section 3.1.1.2 Adult Stage 2 for treatment arm vaccine assignments.

Participants in Cohort D will withhold their MMF/MPA, participants in Cohort E will withhold their MTX, and any participants in Cohort F (BCDT) who are also taking MMF/MPA or MTX will withhold these medications. No randomization will be employed.

A total of 80 participants with a Roche Elecsys® Anti-SARS-CoV-2 S result ≤ 2500 U/mL will be allocated to each arm. In each arm, the number of participants with Roche Elecsys® Anti-SARS-CoV-2 S results ≤ 200 U/mL will be capped at 40 participants; the number of participants with Roche Elecsys® Anti-SARS-CoV-2 S results > 200 U/mL and ≤ 2500 U/mL will be capped at 40 participants.

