4.2.1.2.1 Inclusion and Exclusion Criteria for Adult Stage 2 Newly Recruited Participants

4.2.1.2.1.1 Inclusion Criteria for Adult Stage 2 Newly Recruited Participants

Individuals who meet all of the following criteria are eligible for enrollment as participants in Adult Stage 2:

1. Individuals 18 years of age or older that meet classification criteria [1-6] for SLE, SSc, RA, MS, or pemphigus. If a participant has been diagnosed with more than one autoimmune disease, the participant will be assessed based on the disease that is selected for study entry.
2. Willing and able to sign informed consent.
3. Documented full COVID-19 vaccination (CDC card or documentation in medical records).
4. Received an additional COVID-19 vaccine dose (documented by CDC card or in medical records) that was completed at least 4 weeks prior and no more than 48 weeks prior to the Stage 2 Screening visit.
5. Negative or suboptimal serologic response to a previous COVID-19 vaccine administration in one of the qualifying regimens, defined as an Elecsys® Anti-SARS-CoV-2 S (RBD) negative result or positive result of

≤ 200 U/mL, or a low immune response, defined as an Elecsys® Anti-SARS-CoV-2 S (RBD) result of ≤ 2500 U/mL, within 4 weeks of the Stage 2 Baseline/Week 0 visit.

6. The regimens of COVID-19 vaccination that qualify are as follows:
 - a. 3 doses of the Pfizer-BioNTech COVID-19 Vaccine
 - b. 3 doses of the Moderna COVID-19 Vaccine
 - c. 2 doses of the Janssen COVID-19 Vaccine
 - d. 4 or more doses of a single mRNA vaccine (Pfizer-BioNTech COVID-19 Vaccine OR Moderna COVID-19 Vaccine)
 - e. 3 or more doses of a mixture of mRNA vaccines (Pfizer-BioNTech COVID-19 Vaccine OR Moderna COVID-19 Vaccine)
7. Must be currently taking one of the following IS medications with or without additional disease-related medications: MMF (minimum of 1000 mg per day)/MPA (minimum of 720 mg per day), MTX (minimum of 7.5mg per week), or B cell depleting agents within the past 18 months (such as rituximab, ocrelizumab, or ofatumumab).
 - a. If taking MMF/MPA or MTX, the participant must have initiated therapy at least 8 weeks prior to allocation and be taking the same medications (regardless of dose) as at the time of the initial COVID-19 vaccine regimen. Note: Participants who withheld their IS medications around their initial vaccinations are eligible to participate.

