8.3.2 Screening and Randomization/Allocation

8.3.2.1 Pre-Screening

An optional Pre-Screening visit may be conducted to confirm that a participant has had a negative or suboptimal, or low immune response to initial COVID-19 vaccine regimen prior to Screening. This study will be explained in lay language to each potential participant and his or her parent. Each participant and their parent/guardian will sign informed consent and assent forms, as appropriate to age of the participant, before committing to study Pre-Screening procedures. Pre-Screening procedures at the study site will vary by method of recruitment as outlined below:

Study site personnel are responsible for the following:

1. Consent the participant for an ACV01 Pre-Screening Evaluation.
2. Conduct the rapid result or other antibody testing.
3. Invite the participant to an ACV01 Screening Visit if the result is negative or weakly positive per the site preferred antibody test method.

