Description	S2 Pre-Screening	S2 Screening	S2 Baseline	S2 Vaccine Diary Review Phone Visit	S2 Week 4	S2 Week 12	S2 Week 24	S2 Week 36	S2 Week 48	S2 Early Termination	S2 Unscheduled
Visit Window		-21 Days; At least 7 days prior to Vaccination	Week 0/Day 1	Day 8 – Day 12	+/- 1 week	+/- 2 weeks	+/- 2 weeks	+/- 2 weeks	+/- 2 weeks		
Mechanistic Assessments											
Serum ^a				X		X	X	X	X	X	X
Whole Blood/PBMC/Plasma/DNA				X		X	X	X	X	X	X
RNA Assays				X		X	X	X	X	X	X
Background Immunosuppressive Medication Testing (MTX, MPA)				X							
Study Treatment / Investigational Agent											
Alternative vaccine dose eligibility confirmation				X ^b							
Determine alternative COVID-19 vaccine			X								
mRNA COVID-19 vaccine ^c				X ^b							
Sanofi-GSK COVID-19 vaccine				X ^b							

^aIf a site is conducting optional pre-screening rapid result/antibody testing, the site will review the pre-screening consent with the participant and obtain his/her signature prior to conducting any pre-screening activities. Pre-screening is optional for all participants. The site may send an Elecsys® Anti-SARS-CoV-2 S (RBD) sample to the central lab as one of 3 potential pre-screening tests, as outlined in the ACV01 lab manual.

^bComprehensive physical exams include the following systems (at a minimum): general appearance, skin, head/eyes/ears/nose/neck/throat, respiratory/chest, cardiovascular, abdominal, neurological, & musculoskeletal/extremities.

^cTargeted physical exams will be guided by participant complaints and prior abnormalities.

^dNeurological Exam: for all MS participants and for participants with other diagnoses who have a neurological complaint after Stage 2 Screening.

^eHeight will be collected at Stage 2 Screening only. Weight, temperature, pulse, and blood pressure will be collected at each visit.

^fSolicited AEs will be collected for 7 days post study vaccination. Unsolicited AEs will be collected until 28 days post study vaccination.

^gSAEs, MAAEs, NOCMCs, AESIs, COVID-19 diagnoses, and flares of a secondary autoimmune disease will be collected from Day 1 through the end of the participant's study participation.

^hEligibility confirmed by CDC card or documentation in medical records and results of response to a previous COVID-19 vaccine dose assessed by Elecsys® Anti-SARS-CoV-2 S (RBD) assay.

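### Step 3 of the optional pre-screening for new recruits still invites only negative or weakly positive results, out of line with its own stated purpose and with the 2500 U/mL eligibility ceiling

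*Protocol*

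**What the plan says.** Protocol Section 8.2.2.1.1 (Adult Stage 2, newly recruited) opens with the purpose of the visit: "An optional Pre-Screening visit may be conducted to confirm that a participant has had a negative, suboptimal, or low immune response". Its third step then reads: "Invite the participant to an ACV01 Screening Visit if the result is negative or weakly positive per the site preferred antibody test method". Sections 8.3.2.1 (Pediatric Stage 1) and 8.4.2.1.1 (Pediatric Stage 2, newly recruited) also name low response in the purpose sentence and also end by inviting people "if the result is negative or weakly positive per the site preferred antibody test method".

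Eligibility in these populations goes further. Section 4.2.1.2.1 admits negative or suboptimal responders, "or a low immune response, defined as an Elecsys® Anti-SARS-CoV-2 S (RBD) result of ≤ 2500 U/mL", and Sections 4.2.2.1.1 and 4.2.2.2.1.1 set the same ceiling for children. Section 3.1 defines low response as above 200 and up to 2500 U/mL. Section 3.5 plans 80 participants per arm in Adult Stage 2 and both pediatric stages: at most 40 are at or below 200 U/mL, and the number above "200 U/mL and ≤ 2500 U/mL will be capped at 40 participants".

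The footnotes to the schedules in Section 20.1 add two facts: "Pre-screening is optional for all participants", and "The site may send an Elecsys® Anti-SARS-CoV-2 S (RBD) sample to the central lab as one of 3 potential pre-screening tests", with details left to the lab manual.

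**The concern.** A low response can be a clear positive on most tests, so a rule that invites only negative or weak positives does not obviously reach it. If sites apply the rule as worded, part of the eligible population is never offered Screening.

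This bears on the primary analysis. Protocol Section 13.4.2 tests the Week 4 response proportion separately in the low-response subgroup of each arm, against a null rate of 0.25. Section 13.7 sizes each subgroup at 40 in order to have 33 evaluable. Two things could follow. The stratum could fill slowly. Its members could also be weighted towards the lower end of 200 to 2500 U/mL, so that the proportion describes a narrower group than the criteria define.

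**Working it through.** **1. The passages side by side.**

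| Population | Elecsys ceiling | Purpose of pre-screening | Who is invited |
|---|---|---|---|
| Adult Stage 1 (8.1.2.1) | 200 U/mL | negative or suboptimal | negative or weakly positive |
| Adult Stage 2, new (8.2.2.1.1) | 2500 U/mL | negative, suboptimal or low | negative or weakly positive |
| Pediatric Stage 1 (8.3.2.1) | 2500 U/mL | negative, suboptimal or low | negative or weakly positive |
| Pediatric Stage 2, new (8.4.2.1.1) | 2500 U/mL | negative, suboptimal or low | negative or weakly positive |
| Stage 2 rollovers (8.2.2.1.2, 8.4.2.1.2) | 2500 U/mL | negative, suboptimal or low, on Elecsys | no such step |

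Only in the first row do ceiling, purpose and invitation fit together. In the next three the ceiling and purpose are wider and the invitation is unchanged. The likeliest explanation is that step 3 was left as it stood when entry was widened in version 6.0. That is an inference from the wording.

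**2. Does weakly positive stretch to 2500 U/mL?** The protocol does not define the term. Its own figures make the wide reading strained:
- Section 13.4.4 counts Elecsys results of 0.80 U/mL and above as positive. The ceiling is 2500 / 0.80 = 3125 times that value.
- Section 1.2.1 calls a patient median above 250 U/mL apparently robust.
- The same section gives averages of 2,079 to 4,435 U/mL in healthy people after primary vaccination. The top of the eligible range overlaps these.

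**3. The plan's sample size, reproduced.** Inputs from Sections 13.4.2 and 13.7: one-sided exact binomial test, alpha 0.05, null rate 0.25, alternative 0.50. The critical value r is the smallest count with P(X ≥ r | n, 0.25) ≤ 0.05; power is P(X ≥ r | n, 0.50).
- n = 33: r = 13, exact alpha 0.0484, power 0.919. The stated power of at least 90% is confirmed.
- 40 enrolled with the full 20% dropout: 40 × 0.8 = 32 evaluable, r = 13, power 0.892. There is little slack.

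**4. What a shortfall would do.** The documents give no shortfall, so these values are assumed. Evaluable is 80% of enrolled, rounded down.

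| Enrolled in stratum | Evaluable | r | Power at 0.50 |
|---|---|---|---|
| 40 | 32 | 13 | 0.892 |
| 36 | 28 | 12 | 0.828 |
| 30 | 24 | 11 | 0.729 |
| 20 | 16 | 8 | 0.598 |

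The table shows sensitivity only. Nothing in the documents says which row applies.

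**The case against.** The case on the other side is substantial, and most of it limits the size of the point.

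- **The term is open.** A reader might infer that step 3 excludes low responders. The text does not establish that. The term is undefined, and a site reading it together with the section's purpose could count a low response as weakly positive. What stands is ambiguity, with the literal reading the narrower one.
- **Pre-screening does not decide eligibility.** It is optional. Eligibility rests on the central Elecsys at Screening, and nothing bars someone with a stronger pre-screen result from going there.
- **The tests may have cut-offs.** One of the three permitted tests is the eligibility assay itself, and the lab manual, which is not among these documents, may say how to read the others. It therefore cannot be claimed that no cut-off exists, only that the protocol gives none.
- **Rollovers bypass the step.** They are pre-screened on Elecsys with low response named, and they enter the same Stage 2 arms. This does not help Pediatric Stage 1, which has no rollover route.
- **The consequences are not demonstrated.** A reader might infer that the stratum will miss its 33 evaluable or give an unrepresentative proportion. With no figure for how many sites pre-screen or how they read the term, neither can be asserted.

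A reader might also take half of every arm to be affected. The 40 is a cap, and Adult Stage 1 has no such stratum.

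**Conclusion.** The mismatch is real and minor. In three sections the invitation step conflicts with the section's purpose sentence and with the ≤2500 U/mL criterion. Where a site pre-screens new recruits and applies the step literally, eligible people above 200 U/mL may not be invited. The group at risk is the stratum capped at 40 of 80 per arm in Adult Stage 2 and Pediatric Stages 1 and 2. How much of it is lost cannot be computed.

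Two qualifications apply. Pre-screening comes before randomization, so in Pediatric Stage 1 it would not bias the comparison of continuing with withholding medication. It would change who is represented in that comparison and in the one-sample test against 0.25. Whether a tilt towards lower titres would lower the Week 4 proportion is plausible but not settled by the documents: Section 2.3 lists the association with baseline antibody level as an exploratory question.

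The conclusion assumes that the lab manual does not already correct the step.

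**What to change.** Reconcile step 3 in Sections 8.2.2.1.1, 8.3.2.1 and 8.4.2.1.1 with the eligibility criterion, for example:

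*Invite the participant if the result is consistent with a negative, suboptimal or low immune response (Elecsys ≤2500 U/mL, or the cut-off given in the lab manual for the other permitted tests). A positive result on a test that cannot be related to 2500 U/mL does not by itself preclude Screening.*

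If the lab manual has no cut-offs for the other two tests, they should be added there. Section 8.1.2.1 can stay as it is, since Adult Stage 1 is closed and its ceiling is 200 U/mL.

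The cost is some additional screen failures. These are not free to participants: Adult Stage 2 Screening includes a 31 mL blood draw, infectious disease testing and a full physical examination. A purely qualitative test would also lose most of its use as a filter. Sample size, alpha and analysis do not change.
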